## **13.0 PARTICIPANT SAFETY MEASURES**

### **13.1 Patient Safety Screening**

Even though referral through EIMG and participation in the community-based physical activity program is not part of the research study, we will monitor and track patient safety in the physical activity program as we are tracking participant (effectiveness) outcomes as a part of the study.

### **13.2 Healthcare Provider Screening of Patient**

Prior to receiving an EIMG referral, participants are screened by the ordering provider to determine eligibility in the program. Upon opening the referral order set, the provider is shown a list of conditions that excludes a patient from participating in EIMG. The list of exclusion criteria is as follows:

- Patients <18 years
- Patients >350 lbs (evaluated on a case-by-case basis)
- Obstetric patients
- Patients paralyzed and/or have inability to move
- Patients on daily oxygen use
- Using ambulatory aid (cane, walker, wheelchair, etc.)
- Patients on dialysis
- Patients with several High Risks and/or Comorbidities
- Patients with high-risk behavior health issues: acute suicidal ideation, acute psychiatric or psychological disorders not resolved within 90 days prior to EIMG referral
- Patients receiving chemotherapy within the past 3 months
- Patients with a concurrent referral to PT or OT

Prior to signing the referral, the ordering provider completes a risk severity assessment evaluation of asthma, chronic obstructive pulmonary disease, hypertension, and congestive heart failure to document if the patient has one or multiple of these diagnoses. A patient will become ineligible for the program if any of the listed diagnoses are uncontrolled.

### **13.3 EIMG Care Coordinator Screening of Patients**

The EIMG Care Coordinator will complete a chart review in the electronic health record (EHR) of the patient upon receipt of the referral. The medical history and referral diagnosis will be reviewed to ensure the patient is eligible to participate.

### **13.4 Safety Assessment at the Community PA Facility**

Prior to every physical activity session, patients complete a “Contraindications to Exercise” worksheet (see Appendix B). The EIMG Professional (EIMG Pro) reviews the worksheet and if any signs or symptoms are marked as positive, a safety protocol (Patients Exhibiting Contraindications to Exercise Workflow; see section 13.5) is initiated. If any signs or symptoms develop during the exercise session, the session ends immediately and the EIMG Pro initiates the safety protocol.

### **13.5 Patient Exhibiting Contraindications to Exercise**

If there is a contraindication to exercise, the participant is ineligible to participate in the exercise session or, if already engaged, they will stop the activity immediately. An email will be sent to the Facility Coordinator and the EIMG Care Coordinator with a copy of the “Contraindications to Exercise” worksheet, which will be subsequently uploaded into the patient’s EHR. A message is sent to the referring provider via the EHR messaging system notifying them of the contraindication. An EIMG Release Form is required from the provider for the participant to resume the program.

**13.6 Emergent Events**

In the event of an emergency, the EIMG Pro will follow the facility emergency action plan and then notify the EIMG Care Coordinator. The participant will be evaluated by the referring physician after the acute event. If the patient requires further work-up and is not cleared for exercise, the patient will be released from the program and require another referral in the future if they wish to continue the program. If it is determined the participant may continue, the EIMG Release Form will be completed by the referring provider.

**13.7 Non-Emergent Events**

In the case of a non-emergent event, the EIMG Pro will evaluate the participant to determine the severity of the event. The “Contraindications Worksheet” will be reviewed by the participant if appropriate and the Patients Exhibiting Contraindications to Exercise Workflow will be activated as needed. For mild or moderate events, the EIMG Pro will document the reported symptoms in REDCap.

**13.8 Exercise Session Absences**

Any unplanned absence from an exercise session will require an EIMG Pro to contact the patient by phone if they have not already notified the EIMG team of their absence. The reason for their absence will be documented in REDCap.

## **14.0 HUMAN SUBJECTS PROTECTION**

All requirements relating to obtaining institutional review board (IRB) review and approval and informed consent will be met. Written informed consent will be obtained from each study participant utilizing the local IRB-approved informed consent form. Appropriate research personnel will explain all aspects of the study to each participant, answering all questions and ensuring that all basic elements of the informed consent process are covered. All study personnel will be required to complete Human Subject Protection, Good Clinical Practice and HIPAA training (as required) and will be instructed to act under those guidelines at all times when working with participants, participants data or protected participant health information.

### **14.1 Defining EIMG Research Participants**

The Exercise is Medicine Greenville (EIMG) program (the referral of patients to the community-based physical activity program and their participation in the program) is part of a clinical workflow process that is not considered as a part of the research study. The research study consists of gathering data from surveys, individual interviews with clinic staff and patients that have been referred to EIMG and evaluating the effectiveness of the physical activity program (using data that is already collected as a part of the program). There will be minimal risk to the participants with study activities and all available measures will be taken to protect privacy of participant responses.

### **14.2 The Informed Consent Process**

Prior to consenting to participate in the study, a copy of the informed consent will be mailed or emailed to prospective participants to review ahead of the consent process and to keep as a reference. At a scheduled study meeting, a member of the research staff will explain the study to the potential participant, reviewing all sections of the informed consent in detail and answer any of the participant's questions. During the informed consent process (for all study participants), details of the study will be explained, including participant burden, potential risks and benefits, names and contact information for the study PIs, and other local individuals (i.e., IRB staff) that can be contacted for additional study details. All participants will be asked if they want a copy of the consent form (either a hard or electronic copy) for their personal records. There will be no coercion to participate or prejudice against those who choose not to take part in the study and potential participants will be encouraged to ask any questions they have regarding study procedures. Informed consent will be obtained prior to any participation in the study. Proxy consent will not be accepted as we anticipate that all individuals eligible to participate in the study will be able to provide their own informed consent.

Study participation is voluntary and there are no benefits lost (e.g., ability to participate in the PA program) if an individual declines participation. Individuals who refuse to participate or who withdraw from the study will be treated without prejudice.

The informed consent form will be updated and revised whenever important new safety information is available, or whenever the protocol is amended in a way that may affect a participants' participation in the trial.

### **14.3 Documenting Informed Consent**

#### **14.3.1 Written Informed Consent**

Individuals involved with in-person study activities (e.g., individual interviews) will be asked to provide their written consent by signing and dating the consent form. The person obtaining consent will also sign and date the consent document. The consent must be properly executed and complete to be valid. Another research staff member will review the consent form after it is signed to ensure that the consent is properly executed and complete. The participant will be informed that their participation is voluntary and they may withdraw from the study at any time, for any reason without penalty. Participants will be given the option of having a signed copy of

the informed consent form. The original version will be stored in a secure location at each study site. Members of the research team will inspect the informed consent forms periodically to ensure that correct signatures and dates were obtained on valid informed consent forms.

#### **14.3.2 Verbal Informed Consent**

Individuals conducting virtual study activities (i.e., telephone or virtual interviews) will be asked to provide their verbal consent to participate in the study. The research team member will follow the same informed consent process as with the written informed consent process. However, the participant will not be asked to sign a consent form, only to verbally agree to participate in the study after the informed consent process. The final page of the informed consent form will have a page for documentation of verbal consent that the research team member will check off (if provided) and date.

#### **14.4 Obtaining Participant Consent**

A description of how informed consent will be obtained from study participants is described below:

##### **14.4.1 Individual (Adoption) Interviews with Practice Managers**

All practice managers at clinics eligible to adopt EIMG will receive an email inviting them to participate in an individual (adoption) interview. Practice managers that wish to participate in the individual (implementation) interviews will undergo the informed consent process to obtain either their written (for in-person interviews) or verbal (for virtual interviews) consent immediately prior to conducting the interview.

##### **14.4.2 Online ORCA Questionnaire with Clinic Staff**

All staff at participating clinics that adopted EIMG will receive an email inviting them to complete the online ORCA questionnaire. The email will contain an electronic link to the online questionnaire. The first page of the online questionnaire will be a consent form providing a detailed explanation of the study (both the online survey and the individual (implementation) interview and potential risks of participation. At the bottom of the webpage, participants will be asked to provide their consent to participate in the study before continuing to the online questionnaire. Individuals that do not agree to participate in the study will be thanked for their time and exited from the questionnaire.

##### **14.4.3 Individual (Implementation) Interviews with Clinic Staff**

All staff at participating clinics that adopted EIMG will receive an email inviting them to participate in an individual (implementation) interview. If an individual provided their consent to participate in the online ORCA questionnaire, they will not undergo an additional informed consent process prior to conducting the individual interview as verbiage in the online consent will also describe participation in this individual interview. Eligible clinic staff that did not complete the online ORCA questionnaire will undergo the informed consent process to obtain either their written (for in-person interviews) or verbal (for virtual interviews) consent.

##### **14.4.4 Individual Interviews with Patients**

Patients that received an EIMG referral at a participating clinic will be invited to participate in an individual interview. Patients that wish to participate in the individual interviews will undergo the informed consent process virtually (over the phone) to obtain their verbal consent immediately prior to conducting the phone interview.

#### **14.5 Participant Discontinuation**

Participants will have the right to discontinue study participation at any time. This includes stopping the individual interviews at any time or not responding to questions they do not wish to answer, closing out the online ORCA questionnaire, or declining to have their PA program data included in the research study. Females participating in the PA program who become pregnant

during the study will be required to discontinue participation. Additionally, participants may be asked to stop their participation in the PA program if any situation arises that, in the investigator's judgment, poses a safety risk. Participants who must stop the PA program will not continue completing program assessments.

#### **14.6 Participant Remuneration**

Participants (practice managers, clinic staff, and patients) will receive monetary remuneration (gift cards) for participating in the individual interviews to compensate them for their time, travel, and burden of participation. Clinic staff will not be compensated for completing the online ORCA questionnaire and patients will not be compensated for participating in the 12-week, community-based PA program or any of the program assessments.

## **15.0 REPORTING AND MONITORING**

### **15.1 Statement of Compliance**

This trial will be conducted in compliance with the appropriate protocol, appropriate ICH guidelines (including current Good Clinical Practice [GCP]), the principles of the Declaration of Helsinki, and all other applicable regulatory requirements. Written approval of the study protocol, consent form, other supporting documents, and any advertising for participant recruitment will be obtained by the Prisma Health institutional review board (IRB) prior to study initiation. Any amendments to the protocol or consent materials will be approved before they are implemented. Annual progress reports and Serious Adverse Event (SAE) reports will be submitted to the IRB according to its usual procedures.

### **15.2 Regulatory Files**

The regulatory files should contain all required regulatory documents, study-specific documents, and all communications. Regulatory files will be reviewed for compliance prior to study initiation, throughout the study, as well as at the study closure.

### **15.3 Financial Disclosure**

All investigators will comply with the requirements of 42 CFR Part 50, Subpart F to ensure that the design, conduct, and reporting of the research will not be biased by any conflicting financial interest. Everyone with decision-making responsibilities regarding the protocol will have an up-to-date signed financial disclosure form on file with their respective institutions.

### **15.4 EIMG Exercise Session Monitoring**

Study team members may periodically audit, at mutually agreed upon times, EIMG exercise sessions and source documents for each participant. Monitoring will take place as specified by the research team and occur as often as needed to help prevent, detect, and correct issues at the community PA facilities. Research staff will verify that procedures for the exercise sessions are properly followed and that EIMG Pros are trained and able to conduct the protocol as intended. If the review of exercise session documentation indicates that additional training is needed, research staff arrange for that training.

### **15.5 Study Documentation**

Study documentation includes all exercise session report forms, data correction forms, questionnaires, monitoring logs, sponsor-investigator correspondence, signed protocol and amendments, Institutional Review Committee correspondence, approved consent forms, and signed participant consent forms. Source documents include all (audio) recordings of individual interviews, notations of interviews or exercise sessions, and records necessary for the evaluation and reconstruction of the clinical research study. Whenever possible, the original (audio) recording of an observation should be retained as the source document. Transcripts should provide a clear and exact duplication of the recordings, but are not considered source documentation.

### **15.6 Records Retention and Requirements**

All research records will be stored by the PI in a secure location to be accessed only by authorized research personnel. Study records will be stored in accordance with local IRB, state, and federal regulations and will be kept for a minimum of 3 years following study completion.

### **15.7 Participant Confidentiality/Privacy**

Participant records will be made confidential by using study codes for identifying participants, secure and separate storage of any documents that have participant identifiers, and secure computing procedures for entering and transferring electronic data. All research information obtained on participants is confidential, and disclosure to any third parties without specific authorization is strictly prohibited. To maintain subject privacy, all study forms and reports will

be identified by a coded study identification number only. No subject identifying information will be included in any presentations or publications resulting from the study. Study records may be inspected by the sponsor and its authorized representatives, other government agencies such as the U.S. Department of Health and Human Services (DHHS) Office for Human Research Protections (OHRP), authorized Node Staff, or the local IRB for quality assurance purposes.

### **15.8 Confidentiality Breach**

In the event of a confidentiality breach with our survey and/or interview data, reporting to the site IRB will be done within 10 business days of the co-Principal Investigators (PI) becoming aware of the breach.

### **15.9 Data and Safety Monitoring Board (DSMB)**

As required by the National Institutes of Health (NIH), this study will develop and maintain an IRB-approved data and safety monitoring plan. In discussion with the funding agency (the National Heart, Lung, and Blood Institute), it was determined that an independent DSMB for this study is not necessary for this study. NIH policy states that monitoring activities of all NIH-sponsored or -conducted clinical studies are commensurate with their risks, nature, size, and complexity. Given that the nature of this research study involves conducting individual interviews and online surveys with participants, none of whom would be considered vulnerable subjects, this trial was deemed to be a low-risk behavioral study.

### **15.10 Protocol Deviations & Violations - Reporting and Management**

A protocol departure is any departure from procedures and requirements outlined in the protocol. Protocol departures may occur on two levels, deviation versus violation. The difference between a protocol deviation and violation has to do with the seriousness of the event and the corrective action required. A protocol deviation is considered an action (or inaction) that by itself is not likely to affect the scientific soundness of the investigation or seriously affect the safety, rights, or welfare of a study participant. Protocol violations are departures that may compromise the participant safety, participant rights, inclusion/exclusion criteria or study data and could be cause for corrective actions if not rectified or prevented from re-occurrence. Protocol violations will be monitored for: 1) significance, 2) frequency, and 3) impact on the study objectives, to ensure that violations do not compromise the integrity of the trial. Any protocol deviations that are substantive and affects rights, safety, or welfare of subjects or willingness to continue in study or the integrity of the research data will be reported within 10 business days from the date either of the co-PIs becoming aware. The decision about whether a departure from the protocol will be designated as a protocol deviation or a protocol violation will be made by the multiple PIs.

### **15.11 Adverse Events (AEs)**

#### **15.11.1 Definitions of AEs**

Any unfavorable or unintended medical or psychological event experienced by a study participant. This can represent a new symptom or an exacerbation of an existing condition. The event does not necessarily have to be causally related to the research study intervention.

#### **15.11.2 Classification of AEs**

An AE will be classified as one of the following:

- i. *Mild*: events that do not interfere with the participants daily activities (i.e., muscle soreness, fatigue, anxiety).
- ii. *Moderate*: events that have a low level of inconvenience for the participant. This may cause some interference with EIMG participation but is not a contraindication.
- iii. *Severe*: events that interrupt the normal daily activities of a participant. Events would include, but are not limited to, those listed on the Contraindications to Exercise worksheet.

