### **15.11.3 Reporting of AEs**

Mild and moderate AEs will be documented but need not be reported to the site IRB or sponsor (NHLBI) unless a trend appears. If an adverse event is classified as severe and is expected and related to study participation, IRB guidelines indicate this will be reported periodically (annually).

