**Please circle Y (yes) or N (no) if experienced recently or currently:**

Have you been hospitalized or diagnosed with any new health problems since your last session?	Y/N	Y/N	Y/N	Y/N	Y/N	Y/N	Y/N	Y/N	Y/N	Y/N	Y/N	Y/N	Y/N
Abnormal leg pain or cramps	Y/N	Y/N	Y/N	Y/N	Y/N	Y/N	Y/N	Y/N	Y/N	Y/N	Y/N	Y/N	Y/N
Angina or chest pain	Y/N	Y/N	Y/N	Y/N	Y/N	Y/N	Y/N	Y/N	Y/N	Y/N	Y/N	Y/N	Y/N
Unusual or increased shortness of breath	Y/N	Y/N	Y/N	Y/N	Y/N	Y/N	Y/N	Y/N	Y/N	Y/N	Y/N	Y/N	Y/N
Uncontrolled blood sugar at home	Y/N	Y/N	Y/N	Y/N	Y/N	Y/N	Y/N	Y/N	Y/N	Y/N	Y/N	Y/N	Y/N
Nausea, vomiting or diarrhea in past 24 hours	Y/N	Y/N	Y/N	Y/N	Y/N	Y/N	Y/N	Y/N	Y/N	Y/N	Y/N	Y/N	Y/N
Fever	Y/N	Y/N	Y/N	Y/N	Y/N	Y/N	Y/N	Y/N	Y/N	Y/N	Y/N	Y/N	Y/N
Dizziness or faintness	Y/N	Y/N	Y/N	Y/N	Y/N	Y/N	Y/N	Y/N	Y/N	Y/N	Y/N	Y/N	Y/N
New or increased back or joint pain	Y/N	Y/N	Y/N	Y/N	Y/N	Y/N	Y/N	Y/N	Y/N	Y/N	Y/N	Y/N	Y/N
Patient initials at each session:													
I have read and understood the list of symptoms above and do not exhibit any said symptoms at this time													

Patient signature: \_\_\_\_\_

EIMG® Pro Trainers only:

Did the participant exhibit any unusual symptoms during their exercise session?		Y/N	Y/N	Y/N	Y/N	Y/N	Y/N	Y/N	Y/N	Y/N	Y/N	Y/N	Y/N
---	--	-----	-----	-----	-----	-----	-----	-----	-----	-----	-----	-----	-----

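### Section 15.11.2 defines a severe adverse event by two conflicting tests, so one non-serious event can be both mild and severe and its reporting route is unsettled.

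*Combined protocol and SAP*

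**What the plan says.** Section 15.11.2 sets three grades.

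- Mild: "events that do not interfere with the participants daily activities (i.e., muscle soreness, fatigue, anxiety").
- Moderate: a low level of inconvenience, with the limit "This may cause some interference with EIMG participation but is not a contraindication".
- Severe: "events that interrupt the normal daily activities of a participant", followed by "Events would include, but are not limited to, those listed on the Contraindications to Exercise worksheet".

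The worksheet in Appendix B has nine yes/no items. Chest pain stands beside "Abnormal leg pain or cramps", "Nausea, vomiting or diarrhea in past 24 hours" and "New or increased back or joint pain". Under section 13.4 it is a check made before each session, and any positive item starts the safety workflow of section 13.5.

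Section 13.7 has the exercise professional assess how severe a non-emergent event is. The worksheet is reviewed where appropriate, the workflow is used as needed, and mild or moderate events are entered in REDCap. It gives no grading criteria.

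Section 15.11.3 attaches consequences to the grade: "Mild and moderate AEs will be documented but need not be reported to the site IRB or sponsor (NHLBI) unless a trend appears". A severe event that is expected and related is reported annually.

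**The concern.** A severity grade should place an event on one scale. Here the top grade can be reached in two ways that measure different things: how far the event disturbs ordinary life, and whether it appears on a form that decides if a patient may exercise that day. A screening list is rightly broad and cautious, and for that reason it is a poor measure of intensity.

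Two people applying the protocol correctly could give the same event different grades. The grade sets the reporting route, so the IRB and the sponsor would see some non-serious events and not others according to which sentence the rater followed. Section 13.1 commits the study to tracking safety in the program, and section 15.9 records that there is no independent monitoring board. Consistent grading therefore rests on the study team and the facility staff.

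**Working it through.** No arithmetic applies: the documents attach no event rate to the grades. The check sets the definitions in section 15.11.2 against the Appendix B items and follows each event through to section 15.11.3. All events below are taken to be non-serious, expected and related.

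| Event | Grade by effect on daily activities | Grade by worksheet | Reporting under 15.11.3 |
|---|---|---|---|
| New back pain, daily activities unaffected | Mild | Severe | Documented only, or annual report |
| Abnormal leg cramps, daily activities unaffected | Mild | Severe | Documented only, or annual report |
| Diarrhea within the past day, daily activities unaffected | Mild | Severe | Documented only, or annual report |
| Brief chest pain, daily activities unaffected | Mild | Severe | Documented only, or annual report |
| Muscle soreness, daily activities unaffected | Mild | Not listed | Documented only |
| Unlisted event that interrupts daily activities | Severe | Not listed | Annual report |

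Three steps follow.

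1. The conflict is confined to worksheet items that leave daily activities intact (the first four rows). Unlisted events grade consistently because the list is expressly not exhaustive.
2. Moderate offers no middle ground. It is closed to contraindications, so a listed event goes to one end of the scale or the other. Moderate is also defined by inconvenience and interference with program participation, which is a different scale from the one used for Mild and for the first sentence of Severe.
3. Section 13.7 does not settle the matter. It treats the grade as a judgement about the event and the contraindication workflow as a separate step, whereas section 15.11.2 ties the two together.

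There is ample opportunity for the conflict to arise. Section 4.9 gives two sessions a week for 12 weeks, and section 13.4 requires the worksheet before each, so a patient who attends every session completes 2 × 12 = 24 session screens. Section 4.11 sends some patients to a musculoskeletal and pain module, where back or joint pain is an obvious complaint. How often an item is marked positive is not stated, so the number of affected events cannot be calculated.

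**The case against.** The strongest reply has four parts.

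- **The list may only illustrate the functional test.** The worksheet sentence can be read as giving examples of events that interrupt daily activities, with section 13.7 supplying the judgement. This is a possible reading, but it does not remove the conflict. Several listed items need not interrupt anything, and the limit on Moderate makes contraindication itself a grade boundary.
- **The error is cautious.** Over-grading only moves expected, related events from documentation to an annual report, in a study judged low-risk. That holds for a rater who follows the list. A rater who follows the functional test moves a contraindication event the other way, out of reporting.
- **Important events have other routes.** This stands. Section 15.12 defines serious adverse events by outcome, and sections 13.6 and 15.13 cover emergent events and unanticipated problems. A reader might infer that truly severe events would be lost among minor ones. The documents do not support this for any event with a serious outcome.
- **No analysis depends on the grade.** This also stands. A reader might infer that a severe-event rate would be inflated and the trial's safety conclusion wrong, but section 12 plans no such count or rate. For the annual report, section 15.11.3 requires that a severe event be related, and sections 15.11.4 and 15.13.2 have expectedness and relatedness reviewed weekly.

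A reader might also infer that symptoms marked at the orientation visit would become severe adverse events. Section 15.11.1 describes an adverse event as a new symptom or a worsening of an existing condition, and several worksheet items ask about change. A stable complaint present before the program is therefore not naturally counted.

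**Conclusion.** The concern holds as an internal contradiction in the grading rule, at a minor to moderate level. Section 15.11.2 allows the same non-serious event to be Mild and Severe, section 13.7 adds a judgement without criteria, and section 15.11.3 makes the reporting route depend on the result. Grading and reporting of non-serious events would be inconsistent, and a severe grade could not be interpreted as intensity.

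Serious adverse event reporting and the primary analysis of referral rates are not affected. The conclusion rests on the ordinary reading of the worksheet sentence together with the limit on Moderate. It assumes no rate of positive worksheets, and none should be quoted as evidence of size.

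**What to change.** Reconcile sections 15.11.2, 15.11.3, 13.7 and Appendix B as follows.

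- In 15.11.2, grade Mild, Moderate and Severe by one criterion, the effect on daily activities. Put Moderate on that scale, and remove both the worksheet sentence from Severe and the contraindication limit from Moderate.
- In 13.7, refer to that criterion when the exercise professional judges severity.
- Add a REDCap field to each adverse event: worksheet contraindication, yes or no.
- In 15.11.3, state that this field is tabulated and reported alongside the grade, so that an event marked yes is not left unreported because its grade is low.

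The last two changes are needed. Deleting the worksheet sentence alone would allow chest pain that does not interrupt daily activities to be graded Mild and go unreported unless a trend appeared.

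The safety workflow in section 13.5 and the serious adverse event rules in section 15.12 stay as they are. The cost is protocol wording, one data field and brief staff guidance. The downside is that staff must judge the grade instead of reading it from a list, and must complete one more entry.
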